7.4 Participant Follow-Up

7.4.1 Follow-Up Intervals and Methods

Enrolled participants will have follow-up visits at 1-month, 3 months, 6-months, and 12-months via either in person visit or telephone call. For participants into whom the Pristine™ Catheter was introduced during the index procedure, but procedure success was not achieved, only the procedure eCRF will be collected and limited to the collection of safety events and interventions for up to 30 days.

Follow-up windows will be calculated from the index procedure date. Refer to Section 1.2 for an overview of follow-up window time frames and requirements for each visit. The

following data will be collected and documented on the appropriate eCRF for each follow-up unless otherwise specified for treated participants:

- Hemodialysis Catheter Assessment:
 - Document how the participant has been receiving hemodialysis and document the date of the participant's last HD session.
- Dialysis Session Blood Flow Rate:
 - If dialyzing through the Pristine™ Catheter, document the reported dialysis sessions and details such as date of dialysis session, average blood flow rate, number of line reversals, and length of dialysis session.
- If Needed:
 - Documentation of any protocol deviations that have occurred since the last follow-up.
 - Documentation of occurrence and / or status of AEs since the last follow up (refer to Section 9).
 - Any catheter reinterventions the participant has undergone since the prior follow-up.

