## 2.7 Endpoints

### 2.7.1 Primary Endpoints

#### Primary Safety and Performance Endpoint

This study has a combined Safety and Performance endpoint derived from the Dialysis Outcomes and Practice Patterns Study (DOPPS) data. The combined Primary Endpoint will be overall complications including infectious and non-infectious complications at 3 months.

- Infectious Complications are defined as:

Complications due to any documented diagnosis of access infection requiring medical intervention (managed in an outpatient or inpatient setting) or sepsis as diagnosis in the hospitalization file whether access related or not.

- Non-infectious complications are defined as:

Complication due to any noninfectious cause (thrombosis of the access, fibrin material within or around a catheter, catheter migration, central vein stenosis or thrombosis) requiring a revision procedure to maintain patency or improve access performance (i.e., thrombolysis, angioplasty, or surgical correction) in an inpatient or outpatient setting or removal or abandonment with creation of a new access that was not due to an access-related infection).

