#### Non-infectious complications

Complication due to any noninfectious cause (thrombosis of the access, fibrin material within or around a catheter, catheter migration, central vein stenosis or thrombosis) requiring a revision procedure to maintain patency or improve access performance (i.e., thrombolysis, angioplasty, or surgical correction) in an inpatient or outpatient setting or removal or abandonment with creation of a new access that was not due to an access-related infection.

Subject will be considered as having a non-infectious complication and will be counted as an event if the subject has experienced a device-related non-infectious AE resulting in a re-intervention prior to the subject's end day of investigation period:

- **AE CRF Page:** Start Date of AE  $\leq$  End Day of Investigation period **AND** Relationship to study Device: Equals 'Related' or 'Likely Related' **AND** Was event infectious: Equals No **AND** Did AE Result in a Catheter Re-Intervention: Equals Yes; subject will be considered as a failure at AE start date

For each subject, the number of complications through the investigational duration is estimated as:

$$((\text{Number of observed infectious complications} + \text{Number of observed non-infectious complications}) * 1000) / \text{Length of investigation duration (Days)}$$

Length of investigation duration (Days) is from the date of index procedure to the end day of each subject's investigation period (End day of investigation period – Date of index procedure + 1); the end day of investigational period will be the earliest occurrence date of the following three events:

- If a subject's Pristine™ Catheter is removed due to Kidney Transplant, Transferred to AVG/AVF, Peritoneal Dialysis, Withdrawal of Care, or Other reasons, then the date of removal will be used to calculate the length of investigation duration. That is:
  - **Hemodialysis Catheter Re-Interventions CRF page:** Catheter removal Equals Yes **AND** Reason for catheter removal Equals: Kidney Transplant, Transferred to AVG/AVF, Peritoneal Dialysis, Withdrawal of Care, or Other; date of re-intervention is used in the estimation of investigation duration

$$\text{Length of investigation duration (Days)} = \text{Removal date} - \text{date of index procedure} + 1$$

- If a subject discontinues early, then the discontinuation date will be used to calculate the length of investigation duration.
 

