### 5.3.5 Overall Catheter Survival Rate at 1-month, 3-months, 6-months, and 12-months post-index procedure, defined as the proportion of Pristine™ Catheters that have not been removed for any cause.

#### Binary Analysis

Subject will be considered as a failure of the endpoint for a given visit if the subject has the catheter removed due to infection or catheter dysfunction prior to the upper limit of visit window for the visit:

- **Hemodialysis Catheter Re-interventions CRF Page:** Date of Re-Intervention: <= upper limit of the visit window AND Reason for catheter removal: Equals Infection/Catheter Dysfunction); subject will be considered as a failure at the re-intervention date

If the subject has not become failure and experience one of the following events prior to the lower limit of visit window, then subject will be considered as non-evaluable at the earliest occurrence of following event dates.

- Catheter has been removed due to Kidney Transplant, Transferred to AVG/AVF, Peritoneal Dialysis, Withdrawal of Care, or Other reasons
  - *Hemodialysis Catheter Re-Interventions CRF page: Catheter removal Equals Yes AND Reason for catheter removal Equals: Kidney Transplant, Transferred to AVG/AVF, Peritoneal Dialysis, Withdrawal of Care, or Other*

OR

- Subject has discontinued from the study.

If the subject has experienced any of the above **non-evaluable** events prior to the lower limit of visit window subject will be counted as a non-evaluable for a given visit. Else subject will be considered as a success of the endpoint for a given visit.

The overall catheter survival rate will be reported with 95% confidence interval from the exact binomial method. The analysis will be performed on the mITT population through 1-month, 3-months, 6-months, and 12-months.

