### **Binary Analysis**

Subject will be considered as loss of overall patency if subject has experienced one of the following events:

- Subject undergoes re-intervention and re-intervention date is after the first dialysis session date
  - **Hemodialysis Catheter Re-Interventions CRF:** Date of Re-intervention > **Procedure Overview Details-Part 2 CRF:** Date of first dialysis session and subject will be considered as a failure at re-intervention date
- Subject has not been able to maintain the patency since last visit
  - **Most Recent Dialysis Session Blood Flow Rate CRF:** Was the catheter able to maintain patency since the last visit (Have the ability to achieve a mean dialysis blood flow of  $\geq 300\text{mL/min}$ )? No . The subject will be considered as a failure at Catheter Dysfunction Date

The subject will become a failure at the earlier occurrence of the above two events. If the subject has lost the overall patency prior to the upper limit of visit window subject will be counted as a failure for a given visit.

If the subject has not become failure and experience one of the following events prior to the lower limit of visit window, then subject will be considered as non-evaluable at the earliest occurrence of following event dates.

- Catheter has been removed due to Kidney Transplant, Transferred to AVG/AVF, Peritoneal Dialysis, Withdrawal of Care, or Other reasons  
*Hemodialysis Catheter Re-Interventions CRF page: Catheter removal Equals Yes AND Reason for catheter removal Equals: Kidney Transplant, Transferred to AVG/AVF, Peritoneal Dialysis, Withdrawal of Care, or Other*  
OR
- Subject has discontinued from the study.

If the subject has experienced any of the above **non-evaluable** events prior to the lower limit of visit window subject will be counted as a non-evaluable for a given visit; else subject will be considered as a success for a given visit.

The overall patency rate will be reported with 95% confidence interval from the exact binomial method. The analysis will be performed on the mITT population through 1-month, 3-months, 6-months, and 12-months.

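### SAP 5.2.1 counts non-infectious primary complications only from adverse event records, so a qualifying re-intervention without such a record counts as zero

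*SAP*

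**What the plan says.** **Definition.** Protocol 3.1, SAP 2.7.1 and SAP 5.2.1 give the same text. A non-infectious complication is one with a non-infectious cause that needs a revision procedure, with thrombolysis, angioplasty and surgical correction given as the procedures. The definition also covers "removal or abandonment with creation of a new access that was not due to an access-related infection". It names no form and sets no device-relatedness condition.

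**Counting rule.** Directly below the definition, SAP 5.2.1 narrows the event to a "device-related non-infectious AE resulting in a re-intervention prior to the subject's end day of investigation period". The source is the AE CRF page alone. The AE must start within the investigation period, be rated Related or Likely Related to the device, be marked non-infectious, and satisfy "Did AE Result in a Catheter Re-Intervention: Equals Yes".

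**Use of the Re-Interventions CRF.** In SAP 5.2.1 this page serves the denominator only: for removals due to transplant, AVG/AVF, peritoneal dialysis, withdrawal of care or other reasons, "date of re-intervention is used in the estimation of investigation duration". Two secondary endpoints read failures straight from the same page, with no AE condition. Catheter survival (SAP 5.3.5) uses "Reason for catheter removal: Equals Infection/Catheter Dysfunction". Patency (SAP 5.3.6) fails when "Subject undergoes re-intervention and re-intervention date is after the first dialysis session date".

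**Collection.** Protocol 7.4.1 lists AEs and re-interventions as separate follow-up items, the latter being "Any catheter reinterventions the participant has undergone since the prior follow-up".

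**The concern.** The endpoint turns on whether a procedure or removal was needed, and the study has a page dedicated to exactly that. The primary count does not consult it. An event reaches the numerator only if the site also opens an AE record, rates it as device-related and ticks the re-intervention question. Nothing in the visible text requires an AE record for every re-intervention, or a reconciliation of the two pages before analysis.

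The trial has one arm and a fixed goal, so no control arm would share the same loss of events. A missed event can only lower the observed rate, which favours the device in both the non-inferiority test and the superiority test that follows. The goal was derived from DOPPS using the broader definition, so a narrower count is not a like-for-like comparison.

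**Working it through.** **1. Definition against rule.**

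| Situation within 3 months | Meets the definition? | Counted by SAP 5.2.1? |
|---|---|---|
| Thrombolysis for thrombosis; AE filed, rated Related, flag ticked | Yes | Yes |
| Same, no AE page | Yes | No |
| Same, AE filed but flag not ticked | Yes | No |
| Same, AE rated Unlikely or Not Related | Yes | No |
| Removal for dysfunction with a new access; no qualifying AE | Yes | No |

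**2. One patient traced through.** A catheter is removed for dysfunction on day 20 and a new access is created, with no qualifying AE. Under SAP 5.3.5 the patient is a catheter-survival failure. Under SAP 5.3.6 the patient is also a patency failure if the removal came after the first dialysis session. In the primary endpoint the patient contributes 0 events. Infection and dysfunction are not among the listed removal reasons that end exposure. Unless a discontinuation is recorded, follow-up time runs on to the 3-month visit, capped at day 105. Protocol 7.5 has participants stay until the day of removal, so a recorded discontinuation may stop the clock, but it does not restore the event.

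**3. The plan's own figure.** Inputs from SAP 2.4: expected rate 31.5 and goal 36.5 per 1000 days, one-sided alpha 0.025, power 80%, attrition 15%, stated exposure 12,765 days.

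- Normal approximation: T = [(1.960·√0.0365 + 0.842·√0.0315) / 0.005]² ≈ 10,976 days. Dividing by 0.85 gives about 12,913, within 1.2% of 12,765.
- Exact Poisson at 0.85 × 12,765 = 10,850 days gives 80.3% power.

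The stated exposure therefore reproduces if it is read as already inflated for attrition. This neither supports nor weakens the point; it fixes the exposures used next.

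**4. Sensitivity to missed events.** Let f be the share of all true complications that leave no qualifying AE record, for whatever reason. The documents give no value, so every f is an assumption. The test is the exact one-sided Poisson test.

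- At 12,765 days the count expected at the goal is 0.0365 × 12,765 = 465.9. The test passes with 423 or fewer events, and 423 / 12,765 = 33.1 per 1000 days.
- At 10,850 days it passes with 357 or fewer.
- With a true rate of 36.5, the counted rate is 36.5 × (1 − f):

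| f (assumed) | Counted rate per 1000 days | Chance of passing, 12,765 days | Chance of passing, 10,850 days |
|---|---|---|---|
| 0 | 36.5 | 2.3% | 2.5% |
| 5% | 34.68 | 18% | 17% |
| 10% | 32.85 | 58% | 53% |

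A loss of 5 / 36.5 = 13.7% of events would make a device exactly at the goal appear to run at 31.5.

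**The case against.** The strongest reply is that AE reporting should already capture these events. The AE definition in Protocol 9.1.1 is broad. Protocol 2.3.1 lists occlusion, thrombosis, tip migration, fibrin sheath and venous stenosis among potential complications and AEs, which closely match the causes named in the endpoint. Protocol 9.4 requires all AEs to be entered on the eCRF. On this view, a thrombolysis with no AE page is a reporting failure by the site and not an exclusion directed by the SAP. Monitoring and data management might find it, and SAP Appendix 2 (Derived Data Specification), visible only by title, might contain a matching rule.

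Much of this stands. It makes the undercount conditional and its size unknown. It does not deal with an unticked flag or an AE rated Unlikely or Not Related, where the site has reported and the rule still drops the event. Nor does it put a reconciliation step in the text that governs the primary analysis.

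It is also fair to say that the definition is not purely procedural: it describes a complication that requires a procedure, and the removal limb also needs a new access. An AE with a re-intervention flag is thus a reasonable first source. In one respect the rule is wider than the definition, because Protocol Appendix A defines re-interventions as any additional procedure on the initial catheter. That could add some events, but it does not recover the missed ones.

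A reader might infer that the primary and secondary results contradict each other. The documents do not support that. Patency and catheter survival are different endpoints, and a patient may properly fail one and not another. The point is narrower: an entry that meets the primary definition can be recorded in the study and still not be counted.

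**Conclusion.** The point holds as a gap between the endpoint definition and its counting rule. A re-intervention that meets the definition counts as zero primary complications when it has no AE page, an unticked flag, or an AE rated Unlikely or Not Related, and the error runs in the device's favour.

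Three stronger readings go beyond the documents:

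- That primary events are in fact under-counted. This depends on how sites complete, flag and rate AEs, which cannot be known from the plan.
- That the Re-Interventions CRF is ignored. It is unused in the numerator only; it does end exposure.
- That the loss would consume most of the margin. Taking half of 31.5 as non-infectious and 30% of those as missed gives 31.5 × 0.5 × 0.3 = 4.7 per 1000 days against a margin of 5, but neither share has any basis in the documents.

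What can be said about size is that the test is sensitive. At a true rate of 36.5 and 12,765 days, an assumed 5% or 10% loss of all events lifts the chance of a false pass from 2.3% to about 18% or 58%. Those figures cover losses from every cause, including the relatedness condition. The change is worth making before the 3-month analysis; confidence is medium because Appendix 2 is not visible.

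**What to change.** Amend SAP 5.2.1 before the 3-month analysis:

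- Reconcile the Re-Interventions CRF with the AE page, and state the date window used to match them.
- Count, once per episode, any Re-Interventions entry that meets the protocol definition, whether or not a qualifying AE record exists. Such an entry is a revision procedure for a non-infectious cause to maintain patency or improve access performance, or a removal or abandonment with creation of a new access that was not due to access infection. Keep the new-access condition on removals, so that the count does not exceed the definition.
- Exclude removals for transplant, planned AVF/AVG transfer, peritoneal dialysis and withdrawal of care.
- Report the AE-page-only count as a sensitivity analysis.
- If Appendix 2 already contains such a rule, move it into 5.2.1 or cite it there.

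The cost is SAP wording and a small merge of two pages already collected. The observed rate may come out less favourable to the device.

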4.2 Scientific Rationale for Study Design

The combined safety and performance primary endpoint is compared to a performance goal of 31.5 complications per 1000 catheter days derived from the Dialysis Outcomes and Practice Patterns Study (DOPPS).⁵ The DOPPS data was chosen due to it's significant sample size of tunneled catheters (n=4207) and it's clear definition of non-infectious and infectious complications. DOPPS I-III enrolled 27, 129 participants that provided access data. DOPPS I enrolled within France, Germany, Italy, Japan, Spain, the United Kingdom, and the United States. DOPPS II and DOPPS III enrolled in Australia, Belgium, Canada, New Zealand, and Sweden.⁵ There have been few hemodialysis catheter studies performed in the last 10 years with many lacking sufficient sample size for statistically powered endpoints. The hemodialysis catheter studies that report 'complication' rates or infection rates have a significant variance in definitions. The KDOQI guidelines have stated a need for consistent definitions and outcomes between tunneled catheter studies.⁶ DOPPS is a globally renowned study providing clinically meaningful definitions with a significant sample size not seen in other studies.

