7.5 Participant Investigation Completion and Premature Discontinuation

Following the index procedure, every participant into whom the Pristine™ Catheter was placed should remain in the study until completion of the required follow-up period or until day of remove of the Pristine™ Catheter. The follow-up period for this clinical investigation is 12 months (365 ± 30 days) for participants who had the Pristine™ Catheter successfully placed. An enrolled participant is considered to have completed the study if the participant has completed the formal follow-up period associated with this clinical investigation through the 12-Month follow-up as described in the Schedule of Activities (Section 1.3).

Upon investigation completion or premature discontinuation (in the situations where applicable), the participant's continued care should be administered per SOC at the discretion of the PI and / or their primary care physician.

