16 APPENDICES

Appendix A - Study Definitions

Appendix B - IFU

16.1 Appendix A - Definitions

Term	Definition
Access Censoring Events	Include participant transfer to Peripheral dialysis, kidney transplantation, AVF, AVG, or the event of a participants premature discontinuation in the investigation due to withdrawn consent, withdrawal by PI, LTF, or participant death (refer to abbreviations for definitions).
Active Participant	An investigation participant who has not completed all required investigation follow-up and who has not prematurely discontinued participation in this clinical investigation (refer to Section 6.5) at the timepoint of reference.
Adjunctive Procedure	Procedure(s) completed during the index procedure (prior to leaving the procedure room) as part of SOC procedures. Procedures to ensure HD continuity, as well as procedures to address AEs.
Adverse Device Effect (ADE)	An ADE is an AE that is considered to be related to the use of the Pristine™ Catheter. This includes AEs resulting from insufficient or inadequate IFU, operation, or any malfunction of the Pristine™ Catheter. Additionally, this definition includes any event resulting from use error or from intentional misuse of the Pristine™ Catheter.
Adverse event (AE)	
An AE is defined as any untoward medical occurrence, unintended disease or injury, or untoward clinical signs (including abnormal laboratory findings) in participants, users, or other persons, whether or not related to the Pristine™ Catheter and whether anticipated or unanticipated. For users or other persons, this definition is restricted to events related to the use of the Pristine™ Catheter.
 
Note: Pre-existing conditions should be considered as part of the participant's medical history and should not be reported as an AE unless there is a substantial increase in severity or frequency of the condition, which has not been attributed to natural history.
 
Exacerbation of an existing condition should be reported as an AE if the event meets the CIP definition of an AE.

All Interventions [Post Creation / After First Use]	The number of interventions [post creation / after first use] inclusive of all interventions (facilitation, maintenance, and HD continuity interventions).

Term	Definition

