$$\text{Length of investigation duration (Days)} = \text{Discontinuation Date} - \text{Date of index procedure} + 1$$
- If the subject has not experienced any of the above events prior to the 3-months visit date, then the 3 months visit date will be used to calculate the length of investigation duration; in case of subject having the 3 months visit out of window and after day 105 or the subject misses the 3 months visit, then day 105 will be the end date of investigational period.
 
$$\text{Length of investigation duration (Days)} = \min((3 \text{ months visit date} - \text{date of index procedure} + 1), 105 \text{ days})$$

The analysis will be performed on the mITT population and repeated with per-protocol population as sensitivity analyses.

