### 5.3 Secondary endpoints

#### 5.3.1 Rate of freedom from catheter-related bloodstream infection (CRBSI) defined by 2019 KDOQI Guidelines for CRBSI.

##### Binary Analysis

Subject will be considered as having CRBSI for a given visit if the subject has experienced device-related bloodstream infection prior to the upper limit of visit window for the visit:

- **AE CRF Page:** AE start date  $\leq$  upper limit of the visit window AND Relationship to study Device: Equals 'Related' or 'Likely Related' AND Was event infectious: Equals Yes AND Select Type of Infection: Equals Blood Stream and Were there clinical manifestation and at least 1 positive blood culture with no apparent source: Equals Yes; subject will be considered as a failure at the AE date

If the subject has not become failure and experience one of the following events prior to the lower limit of visit window, then subject will be considered as non-evaluable at the earliest occurrence of following event dates.

- Catheter has been removed due to Kidney Transplant, Transferred to AVG/AVF, Peritoneal Dialysis, Withdrawal of Care, or Other reasons

***Hemodialysis Catheter Re-Interventions CRF page:*** Catheter removal Equals Yes AND Reason for

*catheter removal Equals: Kidney Transplant, Transferred to AVG/AVF, Peritoneal Dialysis, Withdrawal of Care, or Other*

OR

- Subject has discontinued from the study.

Else subject will be considered as a success (freedom from CRBSI) for a given visit.

The rate of freedom from CRBSI will be reported with 95% confidence interval from the exact binomial method. The analysis will be performed on the mITT population through 1-month, 3-months, 6-months, and 12-months.

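### SAP 5.2.1 does not end exposure at catheter removal for infection or dysfunction, so catheter-free days can enter the primary rate's denominator unless discontinuation is dated at removal

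*SAP*

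**What the plan says.** SAP 5.2.1 (under non-infectious complications) divides each subject's complications by the length of an investigation period. That period ends at the earliest of three dates.

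1. Catheter removal for a listed reason: "If a subject's Pristine™ Catheter is removed due to Kidney Transplant, Transferred to AVG/AVF, Peritoneal Dialysis, Withdrawal of Care, or Other reasons".
2. Early discontinuation: "If a subject discontinues early, then the discontinuation date will be used to calculate the length of investigation duration".
3. Otherwise the 3-month visit, capped at day 105: "If the subject has not experienced any of the above events prior to the 3-months visit date".

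SAP 5.3.5, using the same re-interventions form, defines catheter-survival failure by "Reason for catheter removal: Equals Infection/Catheter Dysfunction". Infection and dysfunction therefore have their own removal code, and the Other category in stop 1 does not cover them.

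Protocol 7.5 says that a participant with the catheter placed "should remain in the study until completion of the required follow-up period or until day of remove of the Pristine™ Catheter". In Protocol Appendix A, access censoring events "Include participant transfer to Peripheral dialysis, kidney transplantation, AVF, AVG, or the event of a participants premature discontinuation", where the discontinuation reasons given are withdrawn consent, withdrawal by the PI, loss to follow-up and death. Removal for infection or dysfunction is not among them.

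Protocol 4.2 describes "a performance goal of 31.5 complications per 1000 catheter days". The hypotheses in Protocol 10.5 and SAP 5.2.2 are stated per 1000 patient days.

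**The concern.** The removals left out of stop 1 are the ones most closely tied to the endpoint. Read literally, a subject whose catheter is removed for infection on day 20, and who is not recorded as discontinued that day, keeps adding exposure until the 3-month visit. With the ±15-day window that visit falls between day 75 and day 105, so about 55 to 85 days are added with no Pristine catheter in place.

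The numerator is almost closed during that time. SAP 5.2.1 counts only events rated related or likely related to the device. A non-infectious event must also lead to a catheter re-intervention, which Protocol Appendix A defines as a procedure with the initial catheter. The denominator grows while events cannot, and it grows more the more often catheters fail early. The primary test of 36.5 per 1000 days, and the superiority test that follows it, would both use this denominator.

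SAP 5.3.1 repeats the list of five reasons. A subject whose catheter is removed for dysfunction on day 20 without a bloodstream infection, and who stays in the study, falls through to "Else subject will be considered as a success (freedom from CRBSI) for a given visit" at every later visit. In the Kaplan-Meier analysis that subject stays at risk until the visit day.

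**Working it through.** **The plan's own figures.** Inputs from Protocol 10.2 and SAP 2.4: λ0 = 36.5 and λ1 = 31.5 per 1000 days, one-sided α = 0.025, power 0.80, attrition 15%, exposure 12,765 days, 142 participants at 90 days.

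- Normal approximation: T = (z₀.₉₇₅√λ0 + z₀.₈₀√λ1)² / (λ0 − λ1)² = 10,976 days. Divided by 0.85 this is 12,913, within 1.2% of 12,765.
- Exact Poisson test: 12,765 × 0.85 = 10,850 days gives 80.3% power for non-inferiority and 85.5% for superiority (26.5 against 31.5), matching the stated 80% and 85%.
- 12,765 / 90 = 141.8, hence 142.

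The design is reproduced, so the same exact one-sided Poisson test is used below.

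**Effect of the omitted stop.** The documents give neither the share f removed for infection or dysfunction by 3 months nor the mean removal day m. Both are assumptions here: f = 5% or 10%, m = 30 to 60. Further assumptions are 142 subjects, a 90-day period, no other attrition, no discontinuation filed at removal, no device-related events after removal, and a true rate of 36.5 per 1000 catheter days.

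- Days counted: 142 × 90 = 12,780.
- Catheter days: 142 × [(1 − f) × 90 + f × m].
- Added days: 142 × f × (90 − m).
- Rate as reported: 36.5 × catheter days / 12,780.
- Critical count: the largest c with P(X ≤ c) < 0.025 when X has mean 0.0365 × 12,780 = 466.5. This is 424 events, with attained level 0.0247.
- Actual type I error: P(X ≤ 424) when X has mean 0.0365 × catheter days.

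| f | m | Added days | Catheter days | 36.5 reads as | Type I error |
|---|---|---|---|---|---|
| 5% | 60 | 213 | 12,567 | 35.89 | 0.054 |
| 5% | 45 | 319.5 | 12,460.5 | 35.59 | 0.076 |
| 5% | 30 | 426 | 12,354 | 35.28 | 0.106 |
| 10% | 60 | 426 | 12,354 | 35.28 | 0.106 |
| 10% | 45 | 639 | 12,141 | 34.67 | 0.188 |
| 10% | 30 | 852 | 11,928 | 34.07 | 0.303 |

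If every period ran to day 105 instead of day 90, the ranges over the same values of m would be 0.069 to 0.125 (5%) and 0.163 to 0.383 (10%).

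If discontinuation is always dated on the removal day, stop 2 ends exposure there, no days are added and the level stays at its nominal value.

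**The case against.** A reader might infer that the primary rate is certain to be biased. The documents do not support that. Protocol 7.5 ties the end of participation to the removal day whatever the reason. Protocol 8.1 allows withdrawal by the investigator or sponsor for safety or administrative reasons and ends data collection at discontinuation, and stop 2 of SAP 5.2.1 ends exposure at discontinuation. If sites file discontinuation on the removal day, there is no bias. SAP Appendix 2, the derived data specification, is listed by title only in the text available here and may settle the date.

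This makes the bias conditional but does not close the gap. No available text equates the two dates. A separate removal stop would have little purpose if every removal were a same-day discontinuation, although overlapping stops do occur under an earliest-of rule. Protocol 7.2.1 continues enrolled participants through 12 months. Protocol 7.4.1 asks how hemodialysis is being received and collects flow data only if the Pristine catheter is in use, so visits without it are foreseen.

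The assumed removal shares are also open to challenge. In the feasibility study (Protocol 2.1) all 44 catheters were patent at 30 days and primary patency was 100% at 60 days, which suggests few early dysfunction exchanges. That was one small site. Six device-related infections were reported over 6 months, and the protocol does not say whether any led to removal. The objection limits how firmly any single row of the table can be held.

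Two further inferences go too far. One is that SAP 5.3.2 is distorted to the same degree. An infection or dysfunction that forces removal will usually already be a device-related adverse event, so the subject has failed and later time does not matter. The other is that the benchmark is shown to use a different time base. Only Protocol 4.2 says catheter days, and the source's handling of time after removal cannot be seen here.

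**Conclusion.** The point holds in conditional form. The exposure rule for the primary endpoint omits the removals most closely linked to endpoint events. Followed literally, without a same-day discontinuation record, it lowers the complication rate in the device's favour. Under the stated assumptions the one-sided type I error is about 0.05 to 0.11 with 5% removed and 0.11 to 0.30 with 10% removed (mean removal day 60 to 30), against 0.025. It is unchanged if discontinuation is always dated at removal. The share and timing of removal are assumptions, and the figures also rest on Poisson counts and no device-related events after removal. The direction of the bias does not depend on the assumed share or timing. The effect in SAP 5.3.1 has the same cause but concerns a descriptive endpoint, and the effect in 5.3.2 is small. A primary denominator should not depend on how each site dates a disposition form.

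**What to change.** - **SAP 5.2.1:** end the investigation period at removal of the Pristine catheter for any reason, including Infection/Catheter Dysfunction, and state that the complication that led to removal is still counted.
- **SAP 5.3.1:** in the Kaplan-Meier analysis, censor subjects without CRBSI at removal for any reason. In the binary analysis, treat them as non-evaluable if removal comes before the visit window.
- **SAP 5.3.2:** use the same wording for consistency; little will change.
- **Units:** reconcile catheter days (Protocol 4.2) with patient days (Protocol 10.5 and SAP 5.2.2), and use one term throughout.

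The cost is a wording change and one programming condition, using a removal date and reason already on the re-interventions form. Total exposure falls slightly. In the six scenarios above, exact non-inferiority power at 31.5 per 1000 days would be 0.83 to 0.85, against 0.86 at 12,780 true catheter days, and the attained level returns to 0.022 to 0.024. If discontinuation is already dated at removal, the change costs nothing in the primary analysis.
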